### 8.2 Key Secondary Efficacy Endpoints Analyses

The key secondary efficacy endpoints below will be analyzed using a fixed sequential method in the order they are listed. Secondary efficacy endpoint #1 will only be analyzed if the primary efficacy endpoint analysis results in rejection of the null hypothesis, and subsequent secondary efficacy endpoints will only be analyzed if all prior secondary efficacy endpoint analyses resulted in rejection of the null hypothesis (e.g., secondary efficacy endpoint #3 would only be tested if the primary analyses of the primary and first two secondary efficacy endpoints result in rejection of the null hypothesis). Analyses of subsequent secondary endpoints will continue hierarchically until the first analysis that results in failure to reject the null hypothesis, and some or all of the secondary efficacy endpoint analyses may not be formally performed.

The key secondary efficacy endpoints are as follows:

- 1. PGI-I response (defined as for CGI-I) at Week 4 of Phase 1 relative to Baseline.
- 2. Reduction in IRLS score at Week 4 of Phase 1 relative to Baseline.
- 3. Reduction in MOS-II score at Week 4 of Phase 1 relative to Baseline.
- 4. Reduction in MOS-I score at Week 4 of Phase 1 relative to Baseline.
- 5. CGI-I score at Week 4 of Phase 1 relative to Baseline.
- 6. For subjects assigned to NTX100 in both Phases 1 and 2, reduction in IRLS Question #7 score ("How often do you get RLS symptoms?") from Baseline to Week 8.

PGI-I response at Week 4 of Phase 1 relative to Baseline will be analyzed in the same manner as the primary efficacy endpoint, except that MI methods will not be used if there are missing data.

The reduction in IRLS score at Week 4 of Phase 1 relative to Baseline will be summarized by treatment group using descriptive statistics. The null and alternative hypotheses for this endpoint are as follows:

$$\begin{array}{c} H_0\text{: } \mu_T \leq \mu_S \\ versus \\ H_1\text{: } \mu_T > \mu_S \end{array}$$

where  $\mu_T$  and  $\mu_S$  are the true means for the NTX100 treatment group and the sham control group, respectively. The null hypothesis will be tested using a one-sided, two-sample t-test at the alpha = 0.025 level.

The reductions in MOS-I and MOS-II scores at Week 4 of Phase 1 relative to Baseline will be analyzed in the same manner as the reduction in IRLS score at Week 4 of Phase 1 relative to Baseline.

The CGI-I score at Week 4 of Phase 1 relative to Baseline will be summarized by treatment group using descriptive statistics. The null and alternative hypotheses for this endpoint are as follows:

$$\begin{array}{c} H_0 \colon \mu_T \geq \mu_S \\ versus \\ H_1 \colon \mu_T \leq \mu_S \end{array}$$

where  $\mu_T$  and  $\mu_S$  are the true means for the NTX100 treatment group and the sham control group, respectively. The null hypothesis will be tested using a one-sided, two-sample t-test at the alpha = 0.025 level.

For subjects assigned to NTX100 in both Phases 1 and 2, the reduction in IRLS Question #7 score ("How often do you get RLS symptoms?") from Baseline to Week 8 will be summarized using descriptive statistics. The null and alternative hypotheses for this endpoint are as follows:

$$\begin{array}{c} H_0 \text{: } \mu_{TT} \leq 0 \\ \text{versus} \\ H_1 \text{: } \mu_{TT} \geq 0 \end{array}$$

where  $\mu_{TT}$  is the true mean reduction for subjects who received NTX100 in both Phases 1 and 2. The null hypothesis will be tested using a one-sided, one-sample t-test at the alpha = 0.025 level.

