16.14. Administration of assessments

- PGI-I (Patient Global Impressions Improvement Scale). The subject and not the examiner (site staff) should make the ratings, but the examiner should be available to clarify any misunderstandings the subject may have about the questions. The examiner should mark the subject's answers on the form.
- CGI-I (Clinical Global Impressions Improvement Scale). The CGI-I is completed by the Investigator after reviewing the subject's PGI-I response and conducting a short interview with the subject regarding their RLS symptoms over the past week compared to baseline. The Investigator will not be permitted access to the subject's IRLS responses.

- **Refractory categorization.** The refractory categorization form should be completed by the Investigator, within 72 hours of EVAL 1.
- IRLS. The subject and not the examiner (site staff) should make the ratings, but the examiner should be available to clarify any misunderstandings the subject may have about the questions. The examiner should mark the subject's answers on the form.
- **MOS-Sleep.** The subject and not the examiner (site staff) should make the ratings, but the examiner should be available to clarify any misunderstandings the subject may have about the questions. The examiner should mark the subject's answers on the form.
- Blinding assessment. The subject and not the examiner (site staff) should make the ratings, but the examiner should be available to clarify any misunderstandings the subject may have about the questions. The examiner should mark the subject's answers on the form.
- The **Daily Questionnaire** will be completed by the subject.
- **Subject characterization** will be completed by the examiner (site staff) based on information from the subject.
- **Medical history** will be completed by the examiner (site staff) based on information from the subject.
- For the **Weekly questionnaire**, the subject and not the examiner (site staff) should make the ratings, but the examiner should be available to administer the questions and clarify any misunderstandings the subject may have about the questions. The examiner should mark the subject's answers on the form.

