**Table 1: Schedule of Assessments** 

	EVAL 1	EVAL 2	EVAL 3	EVAL 4	EVAL 5	EVAL 6	EVAL 7	EVAL 8	EVAL 9	EVAL 10	EVAL 11
	Day 0* in-office	Day 3	Day 7	Day 14 in-office	Day 21	Day 28 in-office	Day 31	Day 35	Day 42	Day 49	Day 56 in-office
Informed Consent	X										
Screening	Х										
Subject characterization	Х										
Medical History	Х										
Refractory categorization	Х										
Concomitant Medications	Х			Х		Х			Х		Х
Randomized receipt of	Х										
Treatment or Sham Device											
Begin open-label use of						Х					
Treatment Device											
Daily Questionnaire		Х	Х	Х	Х	Х	Х	Х	Х	Х	Х
follow-up											
Weekly questionnaire and follow-up			Х	Х	Х	Х		Х	Х	Х	Х
CGI-I						Х					Х
PGI-I				Х		Х			Х		Х
IRLS	Х			Х		Х			Х		Х
MOS-Sleep	Х					Х					Х
Custom RLS questionnaire						Х					Х
Blinding Assessment						Х					
Adverse Events		Х	Х	Х	Х	Х	Х	Х	Х	Х	Х

\* If EVAL 1 spans multiple days, Day 0 refers to the final day of EVAL 1.

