### **5.2** Adjustments for Covariates

There will be no adjustment for covariates in any efficacy or safety analysis, unless there are missing data for the primary efficacy endpoint and multiple imputation methods are used (see Section 5.3). Only the logistic regression analysis conducted to assess the blinding will include adjustment for covariates. The dependent variable for this analysis will be the participant's guessed treatment, and the explanatory variables will be the participant's actual treatment and the following two PGI-I Day 28 indicator variables as covariates: (1) being at least "minimally improved" and (2) being at least "much improved".

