### 5.3 Handling of Dropouts and Missing Data

If there are any missing data for the primary efficacy endpoint, multiple imputation (MI) methods will be used to impute the missing data. Using SAS® PROC MI, the logistic regression method of imputation will be used with treatment group and the following covariates as explanatory variables: IRLS at Days 0 and 14 and PGI-I at Day 14. This method of multiple imputation is appropriate for a binary dependent variable with explanatory variables following a monotone missing pattern and assumes that the data for the dependent variable are missing at random (MAR). If the data do not follow a monotone missing pattern, the fully conditional specification (FCS) method will be used to impute missing data. For each imputed dataset, PROC FREQ of SAS® will be used to obtain the responder rate and the corresponding standard error for each treatment. PROC MIANALYZE of SAS® will be used to combine the results from the imputed datasets to produce an overall estimate of the true responder rate and the corresponding 95% confidence interval for each treatment. The estimated difference in true responder rates and the p-values for the test for superiority of NTX100 to sham control from a normal approximation test will also be presented.

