### 8.0 EFFICACY AND SAFETY ANALYSES

### 8.1 Primary Efficacy Endpoint Analysis

The primary efficacy endpoint is the response on the Clinical Global Impressions-Improvement (CGI-I) scale at Week 4 of Phase 1 relative to Baseline (study entry) where a "successful" response is defined as a response of "Much Improved" or "Very Much Improved". This endpoint will be summarized by treatment group using frequencies and percentages. The null and alternative hypotheses for this endpoint are as follows:

 $H_0: RR_T \leq RR_S$ 

versus

 $H_1: RR_T > RR_S$ 

where  $RR_T$  and  $RR_S$  are the true responder rates for the NTX100 treatment group and the sham control group, respectively. The null hypothesis will be tested using a one-sided normal approximation test for the comparison of two proportions at the alpha = 0.025 level. If there are any missing data for this endpoint, multiple imputation (MI) methods will be used to impute the missing data.

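### Key secondaries #1-#5 are planned as observed-case tests inside an ITT analysis, which biases them in either direction if outcome-related dropout differs by arm

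*SAP*

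**What the plan says.** SAP 6.1 makes the ITT population the basis of the primary analysis for all efficacy endpoints. The definition carries an asterisk whose footnote is not in the text available for this review.

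Multiple imputation (MI) is tied to the primary endpoint in three places:
- SAP 5.2 rules out covariate adjustment in efficacy and safety analyses "unless there are missing data for the primary efficacy endpoint and multiple imputation methods are used".
- SAP 5.3 opens: "If there are any missing data for the primary efficacy endpoint, multiple imputation (MI) methods will be used to impute the missing data". Its predictors are treatment, IRLS at Days 0 and 14, and PGI-I at Day 14. It justifies the choice thus: "This method of multiple imputation is appropriate for a binary dependent variable".
- SAP 8.1 repeats for CGI-I response: "If there are any missing data for this endpoint, multiple imputation (MI) methods will be used to impute the missing data".

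SAP 8.2 handles the key secondaries differently. PGI-I response is analysed like the primary "except that MI methods will not be used if there are missing data", with no substitute rule and no stated denominator. For IRLS: "The null hypothesis will be tested using a one-sided, two-sample t-test at the alpha = 0.025 level". The two MOS indices follow IRLS, and CGI-I score gets the same kind of t-test. No missing-data rule is given for any of them.

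The table shells agree. Table 2.1 (primary) has an MI footnote and Table 2.3 (secondaries) has none. Table 2.3 prints an n row under each score, separate from the column N. For PGI-I it has Yes and No rows but no row for missing.

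Protocol 17.1.3 says, for efficacy in general, that MI may be used.

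**The concern.** A two-sample t-test cannot use a subject who has no Week 4 value. The ITT analysis of #2-#5 therefore becomes an analysis of those who stayed, and PGI-I most naturally goes the same way. Randomisation does not protect a comparison of stayers when the reasons for leaving relate to outcome and differ by arm. That is plausible in a trial of a worn device in which sham subjects may see no benefit and active subjects may feel discomfort.

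The supportive analysis does not check this, because the Per Protocol population in SAP 6.2 also removes dropouts and subjects with missing endpoint data. There is also a small internal mismatch: a missing Day 28 CGI-I rating is imputed as a response in the primary, while the same rating drops out as a score in #5.

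At stake are the estimates and formal tests of five key secondaries. Under SAP 5.6, failure at #1 ends formal testing of everything after it.

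**Working it through.** **1. Amount of missing data.** SAP 3.4 plans 15% dropout: 112 / (1 − 0.15) = 131.8, rounded up to 132, which reproduces the planned enrolment. So 132 × 0.15 = 19.8, or about 20 subjects, would be lost over the whole study. The documents do not split this by arm or phase. The scenarios that average 15% below place all of it before Day 28. The 10%/5% scenario averages 7.5%, half of it.

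**2. Assumptions (not in the documents).** 66 per arm; no true effect; 30% responders in each arm; normal Day 14 and Day 28 states with correlation 0.7. 'Outcome-related' means that only the worse half at Day 14 can leave, each with probability 2p, so the arm loses a fraction p. 'Active only' means that sham subjects leave at random.

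**3. Size of the bias.** Let q be the probability of being in the worse half at Day 14 and still a Day 28 responder. Under these assumptions q = 0.046. The responder rate among those who stay is

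(0.30 − 2p × q) / (1 − p).

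- p = 20%: (0.30 − 0.40 × 0.046) / 0.80 = 0.352
- p = 10%: (0.30 − 0.20 × 0.046) / 0.90 = 0.323

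At 20%/10% with both arms outcome-related, the false difference is 0.352 − 0.323 = 0.029. With active only it is 0.352 − 0.300 = 0.052. At 10%/20% with both arms it is −0.029. With equal rate and pattern it is zero.

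**4. Effect on the one-sided test** (nominal 2.5%, 40,000 simulated trials, observed cases, each endpoint taken alone):

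| Dropout active/sham | Outcome-related in | z-test (#1) | t-test (#2-#5) |
|---|---|---|---|
| none | – | 2.6% | 2.5% |
| 15%/15% | both | 2.5% | 2.5% |
| 10%/5% | both | 3.6% | 3.9% |
| 10%/5% | active only | 4.6% | 5.3% |
| 15%/15% | active only | 6.1% | 7.5% |
| 20%/10% | both | 5.2% | 6.2% |
| 20%/10% | active only | 8.9% | 11.2% |
| 10%/20% | both | 1.2% | 0.9% |

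With true PGI-I rates of 50% and 20% (true difference 30 points), the observed-case estimate lies between 29 and 32 points at 10%/5% or 5%/10%, and between 26 and 36 at 20%/10% or 10%/20%.

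**5. What MI recovers.** Imputing from treatment and the Day 14 value gives an error of 2.0-2.9% for a binary or continuous endpoint with its own Day 14 value, across these scenarios: 20%/10% and 10%/5% (both arms or active only), and 15%/15% (both arms). If half the dropouts leave before Day 14, then at 20%/10% the error is 4.8-5.0% (active only) or 3.8-3.9% (both arms).

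MOS and CGI-I have no Day 14 value (SAP "Table 1: Schedule of Assessments"), so MI must lean on PGI-I and IRLS. At 20%/10% active only:
- If dropout follows the endpoint's own unrecorded Day 14 state, MI leaves 9.7%, 8.2%, 5.5% or 3.6% when the recorded measure correlates 0.3, 0.5, 0.7 or 0.9 with that state. Observed cases give 10.5-11.4%.
- If dropout follows the recorded measure, MI gives 2.1-2.6%. Observed cases give 4.2-9.4%.

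**6. PGI-I denominator.** Take 10 missing per arm, with 25 active and 15 sham responders, and a pooled z-test.
- Missing left out: 25/56 − 15/56 = 0.179; SE = √(0.357 × 0.643 × 2/56) = 0.0906; z = 1.97; p = 0.0243 (pass).
- Missing counted as 'No': 25/66 − 15/66 = 0.152; SE = √(0.303 × 0.697 × 2/66) = 0.0800; z = 1.89; p = 0.0291 (fail).

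With 10 missing at random per arm, the two denominators disagree in about 0.02% of trials at true rates of 64% vs 20%, 1.4% at 50% vs 20%, and 3.5% at 45% vs 27%. The first pair is one that fits the plan's PGI-I sample size of 42.

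**The case against.** **Observed-case analysis is a declared choice.** The shells and the express exclusion of MI for PGI-I point to it, and Protocol 17.1.3 leaves MI optional. This stands. A reader might infer a breach of the protocol, or a plan with no discernible rule for these endpoints, and the documents support neither. The point is that the chosen rule is weaker than one the SAP already contains.

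**The error rates are not trial-level error rates.** SAP 5.6 tests #1 only after the primary succeeds, and #5 needs five earlier rejections. This also stands. A reader might take 9-11% as the chance of a false secondary claim, but it is a stand-alone figure from an extreme scenario. A gated figure would need the joint behaviour of the CGI-I and PGI-I ratings. The two are tied ("The CGI-I is completed by the Investigator after reviewing" the PGI-I response, Protocol 16.14), but the documents do not say how closely.

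**The dropout splits are assumed.** True. With equal rate and pattern nothing is inflated, and with heavier outcome-related loss from sham the test is conservative. A reader might infer that the plan favours NTX100; the documents give no dropout split that would show this.

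**The denominator example sits on the boundary.** Conceded. Neither document proposes counting missing as 'No', and a flip is rare at effects near the plan's sizing. It is a matter of clarity, not a likely decider of the trial.

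**MI is only a partial cure.** True for #3-#5 and for early dropout. It still does better than observed cases in the scenarios checked, most clearly for #1 and #2.

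**Conclusion.** The concern holds as a defect of method that should be corrected before unblinding. On the natural reading, key secondaries #1-#5 use only subjects with Week 4 data, although ITT is named as their primary set; the unseen ITT footnote is the one caveat to that reading. If outcome-related dropout differs by arm, bias follows in either direction. Stand-alone error is about 3.6-3.9% at 10%/5% and 5-6% at 20%/10% with both arms affected, about 9-11% at the 20%/10% active-only extreme, about 1% at 10%/20%, and 2.5% when the arms behave alike. These figures rest on the assumed splits, the correlation of 0.7 and dropout confined to the worse half at Day 14, and they are not gated on the primary. The primary analysis is untouched, and endpoint #6 (single arm, Week 8) lies outside this point. The unstated PGI-I denominator is a secondary matter.

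**What to change.** 1. In SAP 8.2, delete the PGI-I exception. Make MI under missing at random (MAR), with the predictors of SAP 5.3, the primary ITT analysis for PGI-I response (logistic, or FCS if the pattern is not monotone) and IRLS reduction (regression method, or FCS). State that all ITT subjects are in the denominator.
2. Apply the same MI to MOS-II, MOS-I and CGI-I score, adding baseline MOS for the two MOS endpoints. State that it corrects these only partly, because none has a Day 14 value. Drawing the CGI-I score within the response category imputed for the primary would keep the two consistent and leave the primary unchanged; this is optional.
3. Amend SAP 5.2, which allows covariates only through imputation of the primary, and SAP 5.3, whose named method suits a binary variable, so that both cover #1-#5. Add a matching footnote to Table 2.3.
4. Keep the observed-case results as supportive.

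The cost is SAP wording and some SAS code, with no new data collection. The downside is reliance on MAR, with residual bias when subjects leave before Day 14.

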Phase 1 (4-wks): Subjects who pass screening will be randomly allocated at a 1:1 ratio to receive Active or Sham treatment throughout the 4-wk duration of Phase 1. The primary and key secondary efficacy endpoints of the study will compare the final week of Phase 1 to study entry ("Baseline"). Phase 2 (4-wks): All subjects who complete Phase 1 will be allocated to receive open-label Active treatment throughout the 4-wk duration of Phase 2. Instructions for device use will remain the same as during Phase 1.

Figure 1: Study Design Flowchart

5. Blinding

Phase 1 will be double-blind. Information about treatment assignment will be concealed from subjects, investigators, and site staff, except as required in cases of safety emergencies. In additional, all sponsor staff interacting directly with the research staff or investigators (e.g. in a monitoring capacity) or subjects (e.g. in a device specialist capacity) will be blinded to the Phase 1 treatment assignment throughout the study (even during Phase 2).

Phase 2 will be open-label. At the beginning of Phase 2, the treatment assignment on each device will be set to Active for all subjects. This will take place without revealing the previous treatment assignment during Phase 1.

Active and sham devices will be physically identical and will provide identical visual feedback during operation. Both active and sham mode will have an initial ramp-up in stimulation intensity lasting

	Clinical Trial	Document #: CT-3 (previously CT-04)
H E A L T H	Investigational Plan, Protocol CT-3	Rev: 2.0 (Superseded Rev A) CC#: 660
		Effective: 6/15/2021

approximately 30 seconds and during which sensations are typically noticeable. No subjects with prior neurostimulation experience with NTX100 or any other neurostimulation devices will be enrolled.

The investigator must contact the sponsor if the need to unbreak blinding arises or within 24 hours of an actual unblinding. The Investigator should not open the unblinding envelop UNLESS knowledge of the subject's treatment assignment is required for the subject's clinical care and safety. Documentation of breaking the blind should be recorded in the subjects Narrative eCRF with the date and time the blind was broken, and the names of the personnel involved.

6. Duration

The study will be completed approximately 18 months after the study opens to accrual or after 132 subjects have been enrolled, whichever occurs first.

7. Study population overview

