### 3.1 Overview

The study consists of a 4-week prospective, randomized, sham-controlled, double-blinded phase (Phase 1) followed by a 4-week prospective open-label phase (Phase 2) for a total of 8-weeks of follow-up per subject. The design of the trial is illustrated in the flowchart below (Figure 1).

Phase 1 (4 weeks): Subjects who pass screening will be randomly allocated at a 1:1 ratio to receive Active or Sham treatment throughout the 4-week duration of Phase 1. The primary endpoint and key secondary efficacy endpoints #1-5 will compare the final week of Phase 1 to study entry ("Baseline").

Phase 2 (4 weeks): All subjects who complete Phase 1 will be allocated to receive open-label Active treatment throughout the 4-week duration of Phase 2. Key secondary efficacy endpoint #6 will compare the final week of Phase 2 to Baseline among subjects who receive Active treatment during both Phase 1 and Phase 2.

Figure 1: Study Design Flowchart

The schedule of assessments for this study is presented in Table 1.

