### 4.2 Key Secondary Efficacy Endpoints

The key secondary efficacy endpoints are as follows:

- 1. PGI-I response (defined as for CGI-I) at Week 4 of Phase 1 relative to baseline.
- 2. Reduction in IRLS score at Week 4 of Phase 1 relative to Baseline.
- 3. Reduction in MOS-II (Medical Outcomes Study Sleep Problems Index I) score at Week 4 of Phase 1 relative to Baseline.
- 4. Reduction in MOS-I (Medical Outcomes Study Sleep Problems Index II) score at Week 4 of Phase 1, relative to Baseline and compared between study arms.
- 5. CGI-I score at Week 4 of Phase 1 relative to Baseline.
- 6. For subjects assigned to NTX100 in both Phases 1 and 2, reduction in IRLS Question #7 score ("How often do you get RLS symptoms?") from Baseline to Week 8.

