### 6.0 ANALYSIS POPULATIONS

### 6.1 Intent-to-Treat (ITT) Population

The Intent-to-Treat (ITT) Population will include all eligible subjects who pass screening and are randomized into the study.\* The ITT Population Set will be used for the primary analysis of all efficacy endpoints, and subjects will be analyzed based on the treatment to which they are randomized.

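### Key secondary #6 is labelled ITT but its hypothesis is defined on subjects treated in both phases, and the SAP has no missing-data rule for it, so the reported mean Q7 reduction may be too large if leavers benefit less

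*SAP*

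**What the plan says.** Endpoint #6 was added by the SAP (section 3.5). It is a within-arm comparison with zero: "The null hypothesis will be tested using a one-sided, one-sample t-test at the alpha = 0.025 level". Its population is described in three ways.

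- **All randomized.** SAP 6.1 states that "The ITT Population Set will be used for the primary analysis of all efficacy endpoints", as randomized, and that this set "will include all eligible subjects who pass screening and are randomized into the study". Table 2.3, titled for the ITT Population, carries #6 as row 6 with a p-value.
- **Assigned.** SAP 4.2 defines the endpoint as "For subjects assigned to NTX100 in both Phases 1 and 2, reduction in IRLS Question #7 score", and the lead-in in 8.2 also uses *assigned*.
- **Received.** SAP 3.1 describes the comparison as one "among subjects who receive Active treatment during both Phase 1 and Phase 2", and 8.2 defines the parameter under test as one that "is the true mean reduction for subjects who received NTX100 in both Phases 1 and 2".

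Entry to Phase 2 is conditional. Both SAP 3.1 and Protocol section 4 (Study Design) provide that "All subjects who complete Phase 1 will be allocated to receive open-label Active treatment". On missing data, SAP 5.3 specifies multiple imputation for the primary endpoint only, and 8.2 rules it out for PGI-I. No rule is given for #6. Protocol 17.1.3 says in general terms that multiple imputation may be used, without committing to it for any endpoint.

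**The concern.** Two separate mechanisms remove subjects from a row headed ITT. An NTX100 subject who leaves in Phase 1 is in the 6.1 set but, on the *received* wording, outside the mean that 8.2 tests. A subject who leaves in Phase 2 stays in the definition but has no Week 8 value and no rule for supplying one.

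If leavers did worse than stayers, the reported mean reduction is larger than the mean for everyone randomized to NTX100, while the table title tells the reader it is the latter. The Per Protocol table does not reveal the difference, because SAP 6.2 also excludes dropouts and subjects with missing endpoint data, so both tables omit the same leavers. Two programmers could also follow the SAP faithfully and report a different n and mean for this row.

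This is distinct from the absence of a sham comparison for #6. It would matter even if the row were read only as a within-arm estimate.

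**Working it through.** **Inputs from the documents.** 66 randomized per arm (Protocol synopsis); 112 completers needed, 15% dropout and 132 enrolled (SAP 3.4); one-sided alpha 0.025, one-sample t-test against zero (SAP 8.2). No expected mean, SD or sample size is given for #6.

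**Step 1: the plan's own figure.** 112 / (1 − 0.15) = 131.8, rounded up to 132. The stated enrolment reproduces.

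**Step 2: how many NTX100 subjects contribute.** 66 × 0.85 = 56.1, so about 56 with Week 8 data and 10 without. This assumes that the 15% applies equally to both arms and runs to Day 56. The SAP does not say which time point *completed* refers to, nor does it split dropout by phase.

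**Step 3: effect on the mean.** Let f be the leavers' mean reduction as a fraction of the completers'. The completer mean divided by the all-randomized mean is 66 / (56 + 10f).

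| Leavers' mean reduction | Calculation | Completer mean vs all 66 |
|---|---|---|
| Worsening by half the completers' reduction (f = −0.5) | 66/51 | +29.4% |
| None (f = 0) | 66/56 | +17.9% |
| Half (f = 0.5) | 66/61 | +8.2% |
| Equal (f = 1) | 66/66 | 0% |
| Larger (f = 1.25) | 66/68.5 | −3.6% |

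At other dropout rates, for f = 0 and f = 0.5: 5% (63 and 3 subjects), +4.8% and +2.3%; 10% (59 and 7), +11.9% and +5.6%; 20% (53 and 13), +24.5% and +10.9%.

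**Step 4: effect on the test.** Assume a completer SD of 1 (not in the documents).

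- Completer mean 0.30: t = 0.30 × √56 = 2.25 (p = 0.0144).
- Adding ten zeros: mean = 56 × 0.30 / 66 = 0.2545. Sum of squares about that mean = 55 + 56 × 0.09 − 66 × 0.2545² = 55.76. SD = √(55.76/65) = 0.926. t = 0.2545 × √66 / 0.926 = 2.23 (p = 0.0145).
- Completer mean 0.50: t = 3.74 for completers and 3.68 with zeros.

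Filling with a constant also shrinks the SD. If the ten leavers instead had mean zero with SD 1, the sum of squares is 55.76 + 9 = 64.76, the SD is 0.998 and t = 2.07 (p = 0.021), still below 0.025. Reversing the decision takes a result already near the threshold and leavers who got worse. With leavers at mean −0.15 and SD 1, the mean is (16.8 − 1.5)/66 = 0.2318. The sum of squares is 55 + 5.04 + 9 + 0.225 − 66 × 0.2318² = 65.72, the SD is 1.006 and t = 1.87 (p = 0.033).

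**The case against.** The strongest reply is that *assigned to NTX100 in both phases* is simply an arm label. Everyone gets Active in Phase 2, so the phrase separates the NTX100 arm from the Sham-then-NTX100 arm. SAP 9.0 uses the two descriptions as a pair, Tables 2.5 and 2.7 carry them under ITT titles, and the Table 2.3 footnote for variable 6 does not mention receipt in both phases. With 6.1, the likely intent is the whole randomized NTX100 arm, loosely worded in 3.1 and in the parameter definition. That is a fair reading of *assigned*. It does not remove the *received* wording from the hypothesis itself, and it leaves the Week 8 gap unfilled.

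Three further points stand. The missing-data gap is not peculiar to #6, since no imputation is specified for the other key secondaries either. Table 2.3 prints a row-level n, so the loss would be visible. And #6 is last in the sequence, so no later test depends on it.

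A reader might infer that the mean *is* overstated. The documents do not support that, because nothing in them says how leavers' Q7 scores compare with completers'. A reader might also infer that entry to Phase 2 depends on response. It depends on completing Phase 1. Protocol 16.16 lists withdrawal of consent, adverse events, non-compliance, pregnancy and medication change among the reasons for removal, and lack of effect is not named. Some of these could track a poor outcome. However, the same list includes no longer meeting the inclusion criteria, and inclusion criterion 4 is itself a Q7 score of 2 to 4, so a literal reading could remove improvers instead.

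**Conclusion.** The inconsistency is in the visible text and should be resolved. As written, following the SAP yields a mean over subjects with Week 8 data under an ITT heading. That mean may exceed the all-randomized mean by about 8% to 18% if 15% of the arm lack Week 8 data and had half or none of the completers' reduction. There is no excess if they did equally well, and a small shortfall if they did better. The range rests on an assumed equal dropout by arm through Day 56 and on unobserved leaver outcomes. It cannot be attributed to the definition alone, because it pools Phase 1 leavers (definition) with Phase 2 leavers (missing data).

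It would be tempting to conclude that the p-value for #6 is unreliable. The calculations do not bear that out. Under an assumed SD of 1 the test against zero barely moves when leavers are given zero reduction, and it changes decision only in a near-threshold case with leavers who worsen. The concern is the size of the reported estimate and what it is called.

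One caveat: the ITT definition in 6.1 carries an asterisk whose footnote is not visible in the copy reviewed. It should be checked for a qualifier.

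**What to change.** In SAP 3.1, 4.2 and 8.2, use one population and one term: define #6 and its tested mean for all subjects randomized to NTX100 (the 6.1 ITT set), whether or not they entered Phase 2.

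Add a missing-data rule for this endpoint: multiple imputation of Week 8 Q7 from Q7 at Days 0, 14, 28 and 42. The schedule of assessments already collects the IRLS at those visits, and Listing 2.3 holds the item scores. The imputation method should suit an item score, not the binary logistic model of 5.3.

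Report zero reduction for leavers as a sensitivity analysis only. As a main rule it would be a single imputation resting on an untested assumption.

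Show the both-phases-received subset as a separately labelled supportive row. It does not belong in Table 2.4, which is the Per Protocol table and also excludes subjects for low device use, medication change, missed follow-ups and other deviations.

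The cost is a wording change in three sections, one extra imputation step and one extra table row. The reported mean reduction may come out slightly smaller.
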